4.2.6 Concomitant Medications

4.2.6.1 Corticosteroids: Patients receiving corticosteroids who have not been on a stable or decreasing dose of corticosteroid for at least 7 days prior to enrollment are not eligible. If used to modify immune adverse events related to prior therapy, ≥ 14 days must have elapsed since last dose of corticosteroid (See [Section 4.1.6.1.d](#)).

4.2.6.2 Investigational Drugs: Patients who are currently receiving another investigational drug are not eligible.

4.2.6.3 Anti-cancer Agents: Patients who are currently receiving other anti-cancer agents are not eligible.

4.2.6.4 Anticonvulsants: Patients must not have received enzyme-inducing anticonvulsants for at least 7 days prior to enrollment (see [Appendix V](#) for a list of enzyme-inducing and non-enzyme-inducing anticonvulsants).

4.2.6.5 Anti-GVHD agents post-transplant:

Patients who are receiving cyclosporine, tacrolimus or other agents to prevent graft-versus-host disease post bone marrow transplant are not eligible for this trial.

4.2.6.6 Patients who are receiving any investigational agent other than pevonidistat, including but not limited to androgens, supraphysiologic doses of corticosteroids, erythropoietin, eltrombopag, or romiplostim.

4.2.7 Drug Interaction:

Patients who have received drugs that are strong inducers of CYP3A4 within 14 days prior to study enrollment are not eligible. See [Appendix VII](#) for more details.

While on study, concomitant use of strong CYP3A4 inhibitors (see [Appendix VII](#)), BCRP inhibitors (cyclosporine, eltrombopag, gefitinib), and UGT1A1 inhibitors (diclofenac, ketoconazole, probenecid, silybin, nilotinib, and atazanavir) should be avoided because of potential for increased irinotecan toxicity.

4.2.8 Infection: Patients who have an uncontrolled infection are not eligible.

4.2.9 Patients who have received a prior solid organ transplantation are not eligible.

4.2.10 Patients with known human immunodeficiency virus (HIV) seropositive are not eligible.

4.2.11 Patients with known hepatitis B surface antigen seropositive or known or suspected active hepatitis C infection are not eligible. **NOTE:** Patients who have isolated positive hepatitis B core antibody (i.e., in the setting of negative hepatitis B surface antigen and negative hepatitis B surface antibody) must have an undetectable hepatitis B viral load. Patients who have positive hepatitis C antibody may be included if they have an undetectable hepatitis C viral load.

4.2.12 History of allergic reactions attributed to compounds of similar chemical or biologic composition as the study agents.

4.2.13 Patients who in the opinion of the investigator may not be able to comply with the safety monitoring requirements of the study are not eligible.

5.0 TREATMENT PROGRAM

5.1 Overview of Treatment Plan

Cycle 1							
Cycle Day							
1	6	8	9	10	11	12	28
Cefixime (Days 6 – 15, 27 – 28) ----->							
		TEMO	TEMO	TEMO	TEMO	TEMO	Eval
		IRIN	IRIN	IRIN	IRIN	IRIN	
Pevonedistat		Pevonedistat		Pevonedistat		Pevonedistat	
		PCP prophylaxis					
IRIN: Irinotecan; TEMO: temozolomide							

Cycle 2 and beyond							
Cycle Day							
-1	0	1	2	3	4	5	21
Cefixime (Days -1 to 8, 20 – 21) ----->							
		TEMO	TEMO	TEMO	TEMO	TEMO	Eval
		IRIN	IRIN	IRIN	IRIN	IRIN	
		Pevonedistat		Pevonedistat		Pevonedistat	
		PCP prophylaxis					
IRIN: Irinotecan; TEMO: temozolomide							

See [Appendix XIII](#) for Therapy Delivery Maps for Cycle 1 and all subsequent cycles.

A cycle of therapy is considered to be 28 days for Cycle 1 and 21 days for Cycle 2 and subsequent cycles. Therapy will be discontinued if there is evidence of progressive disease or drug related dose-limiting toxicity that requires removal from protocol therapy. Patients may continue on protocol therapy for up to 17 cycles (approximately 12 months).

Pevonedistat will be administered intravenously over 60 minutes on Days 1, 8, 10, and 12 of Cycle 1 and on Days 1, 3, and 5 of Cycles 2+ (starting dose is 15 mg/m² [Dose Level 1]).

Cefixime will be administered starting at least two days prior to the start of irinotecan, during, and 3 days after the last dose of irinotecan of each cycle for a total of at least 10 days.

- For Cycle 1, cefixime will be administered on Days 6-15 and Days 27-28.
- For Cycles 2+, cefixime will be administered on Days -1 through 8 and Days 20 through 21.

Days 27 and 28 of Cycle 1 are the same as Days -1 and 0 of Cycle 2. Days 20 and 21 of Cycles 2+ are the same as Days -1 and 0 of subsequent cycles.

Drug doses should be adjusted based on the BSA calculated from height and weight measured within 7 days prior to the beginning of each cycle.

Method of Administration: Patients with solid tumors, including CNS tumors and lymphoma, will receive pevonedistat IV over one hour. In Cycle 1, pevonedistat will be administered as a single agent on Day 1 and in combination with oral temozolomide and IV irinotecan on Days 8, 10, and 12. In Cycles 2+, pevonedistat will be administered in combination with oral temozolomide and IV irinotecan on Days 1, 3, and 5 (see [Appendix IV](#) for temozolomide dosing nomogram and [Section 9.4.4](#) for administration instructions for patients who cannot swallow temozolomide capsules whole). Irinotecan is administered

over 90 minutes one hour after temozolomide. Pevonedistat is administered over 60 minutes at the completion of irinotecan infusion. If emesis occurs within 30 minutes of taking a dose of temozolomide, then the dose may be repeated once. If emesis occurs after 30 minutes, the dose should not be repeated.

CYCLE 1:

Temozolomide: 100 mg/m²/dose (maximum dose 200 mg) PO daily x 5 on Days 8-12. See [Appendix IV](#) for BSA-based dosing nomograms using oral capsules.

Irinotecan: BSA-based dosing (below), IV over 90 minutes daily x 5 on Days 8-12 one hour after temozolomide.

IRINOTECAN IV 50 mg/m ² dose level	
BSA (m ²)	Dose (mg)
0.25-0.29	8
0.3-0.34	12
0.35-0.39	15
0.4-0.44	18
0.45-0.49	22
0.5-0.54	24
0.55-0.59	28
≥ 0.6	50 mg/m ²

Pevonedistat*: IV over 60 minutes on Day 1 alone and on Days 8, 10, and 12 immediately after irinotecan. Starting dose is 15 mg/m² (Dose Level 1). See Dose Escalation Schema in [Section 5.4](#).

For infusion-related reactions consider premedication with diphenhydramine for subsequent doses and increasing infusion duration to 2 hours. Other supportive care measures may be used at the investigator's discretion.

CYCLES 2+:

Temozolomide: 100 mg/m²/dose (maximum dose 200 mg) PO daily x 5 on Days 1-5. See [Appendix IV](#) for BSA-based dosing nomograms using oral capsules.

Irinotecan: BSA-based dosing (below), IV over 90 minutes daily x 5 on Days 1-5 one hour after temozolomide.

IRINOTECAN IV 50 mg/m ² dose level	
BSA (m ²)	Dose (mg)
0.25-0.29	8
0.3-0.34	12
0.35-0.39	15
0.4-0.44	18
0.45-0.49	22
0.5-0.54	24
0.55-0.59	28
≥ 0.6	50 mg/m ²

Pevonedistat*: IV over 60 minutes on Days 1, 3, and 5 immediately after irinotecan. Starting dose is 15 mg/m² (Dose Level 1). See Dose Escalation Schema

in [Section 5.4](#).

For infusion-related reactions consider premedication with diphenhydramine for subsequent doses and increasing infusion duration to 2 hours. Other supportive care measures may be used at the investigator's discretion.

***NOTE:** If pevonedistat dosing is delayed, a minimum of 1 full calendar day between any 2 doses should be maintained. In Cycles 2+, a maximum of 3 doses of pevonedistat should not be exceeded.

Diarrhea prophylaxis: Cefixime or an available equivalent antibiotic will be used as diarrheal prophylaxis during all cycles. Cefixime (8 mg/kg/day as a single daily dose; maximum daily dose 400 mg) or Cefpodoxime (10 mg/kg/day, divided in two oral doses; maximum daily dose 400 mg for children < 12 years and maximum daily dose 800 mg for children \geq 12 years) will be administered starting at least two days prior to the start of irinotecan and continuing for 3 days after the last dose of irinotecan of each cycle for a total of 10 days.

Diarrhea treatment: See [Appendix VIII](#).

Pneumocystis (PCP) prophylaxis: Patients must receive PCP prophylaxis starting on Cycle 1 Day 8, twice daily for 3 consecutive days a week (i.e., BID Friday, Saturday, and Sunday) every week, or per institutional practice, until the end of protocol therapy.

5.2 Criteria for Retreatment and Dose Delays

If pevonedistat dosing is delayed, a minimum of 1 full calendar day between any 2 doses should be maintained. In Cycles 2+, a maximum of 3 doses of pevonedistat should not be exceeded.

5.3 Criteria for Starting Subsequent Cycles

After Cycle 1 which is 28 days, a cycle may be repeated every 21 days if the patient has at least stable disease and has again met laboratory parameters as defined in the eligibility section, [Section 4.0](#) or eligible to continue agent administration per the requirements in [Section 6.0](#).

5.4 Dose Escalation Schema

5.4.1 Part A1: Inter-Patient Escalation

The starting dose will be 15 mg/m² (Dose Level 1) with dose levels for subsequent groups of patients as follows:

Dose Level	Pevonedistat Dose (mg/m ²)	Day(s) of Administration Cycle 1	Day(s) of Administration Cycles 2+
-1	10	1, 8, 10, 12	1, 3, 5
1*	15	1, 8, 10, 12	1, 3, 5
2	20	1, 8, 10, 12	1, 3, 5
3	25	1, 8, 10, 12	1, 3, 5
4	35	1, 8, 10, 12	1, 3, 5

* Starting Dose Level

If the MTD has been exceeded at the first dose level, then the subsequent cohort of patients will be treated at a dose of 10 mg/m² (Dose Level -1). If Dose Level -1 is not well tolerated, further de-escalation will not occur. The study will be closed

to accrual.

5.4.2 Part A2: Inter-Patient Escalation

Patients enrolling on Part A2 of the study will enroll one dose level behind the dose level at which patients in Part A1 are enrolling. Part A2 will open to enrollment on Dose Level 1 once Part A1 has escalated to Dose Level 2. Once the MTD is determined in Part A1, patients may enroll onto the Part A1 MTD. If at any time 2 or more evaluable patients at a lagging dose level experience a DLT, Part A2 will close to further accrual.

5.4.3 Intra-Patient Escalation

Intra-patient dose escalation is not allowed.

5.5 **Grading of Adverse Events**

Adverse events (toxicities) will be graded according to the NCI Common Terminology Criteria for Adverse Events (CTCAE) version 5.0. All appropriate treatment areas should have access to a copy of the CTCAE version 5.0. A copy of the CTCAE version 5.0 can be downloaded from the CTEP web site http://ctep.cancer.gov/protocolDevelopment/electronic_applications/ctc.htm. Any suspected or confirmed dose-limiting toxicity should be reported immediately (within 24 hours) to the Study Chair.

5.6 **Definition of Dose-Limiting Toxicity (DLT)**

DLT will be defined as any of the following events. The DLT observation period for the purposes of dose-escalation will be the first cycle of therapy. Refer to [Section 6.3](#) for specific criteria for patients < 12 months of age at the time of the non-hematological DLT.

Dose limiting hematological and non-hematological toxicities are defined differently.

5.6.1 Non-hematological dose-limiting toxicity for patients \geq 12 months of age:

5.6.1.1 All Grade 3 or greater non-hematological toxicity not clearly related to the underlying disease and attributable to protocol therapy will be considered a DLT except:

- Grade 3 nausea and vomiting < 3 days duration
- Grade 3 elevation of ALT/AST/bilirubin, that returns to Grade ≤ 1 or baseline prior to the time for the next treatment cycle.
NOTE: For the purposes of this study the ULN for ALT is defined as 45 U/L and for AST is defined as 50 U/L. Adverse event grades will be based on increases above the upper limit of normal, regardless of the subject's baseline. See [section 5.6.3](#) and [6.2.4](#). See [Appendix III](#) for nomogram.
- Grade 3 hypophosphatemia (See [section 6.2.5](#)), hypokalemia, hypocalcemia or hypomagnesemia responsive to supplementation.
- Grade 3 arthralgia/myalgia that returns to Grade ≤ 1 prior to the start of the next cycle or within 14 days of optimizing oral analgesics (whichever is shorter).

5.6.2 Non-hematological dose-limiting toxicity for patients < 12 months of age:

5.6.2.1 Any \geq Grade 2 non-hematological toxicity not clearly related to the underlying disease and attributable to the protocol therapy will be considered a DLT with the specific exclusion of Grade 2 liver enzyme

elevation, including ALT/AST/bilirubin, that returns to Grade ≤ 1 or baseline prior to the time for the next treatment cycle.

NOTE: For the purposes of this study the ULN for ALT is defined as 45 U/L and for AST is defined as 50 U/L. Adverse event grades will be based on increases above the upper limit of normal, regardless of the subject's baseline. See [Appendix III](#) for toxicity grading table.

5.6.2.2 Other pevonedistat-related non-hematologic toxicities Grade 2 or greater that, in the opinion of the investigator, require dose reduction or discontinuation of therapy with pevonedistat.

5.6.3 Non-hematological toxicity that causes a delay of ≥ 14 days between treatment cycles.

NOTE: Allergic reactions that necessitate discontinuation of study drug will not be considered a dose-limiting toxicity.

5.6.4 Hematological dose limiting toxicity

5.6.4.1 Hematological dose limiting toxicity attributable to protocol therapy is defined as:

- Grade 4 neutropenia for > 7 days.
- Grade 4 anemia unexplained by underlying malignancy.
- Platelet count $< 25,000/\text{mm}^3$ on 2 separate days, or requiring a platelet transfusion on 2 separate days, within a 7 day period.
- Myelosuppression that causes a delay of > 14 days between treatment cycles.

NOTE: Grade 3 or 4 febrile neutropenia will not be considered a dose-limiting toxicity.

6.0 DOSE MODIFICATIONS FOR ADVERSE EVENTS

The Study Chair must be notified of any dosage modification or use of myeloid growth factor.

6.1 Dose Modifications for Hematological Toxicity (all age cohorts)

6.1.1 Patients who have dose-limiting neutropenia (Grade 4 neutropenia of > 7 days duration or delay in the start of the next cycle for > 14 days due to neutropenia) with no other dose-limiting toxicity should receive the same doses in the next cycle with myeloid growth factor support 24-48 hours after completion of irinotecan, temozolomide, and pevonedistat. Patients MUST NOT receive growth factor in the **first** cycle. If dose-limiting neutropenia recurs after myeloid growth factor is added, start the next cycle with a decrease in temozolomide to 75% of the original dose (75 mg/m²/dose) on Days 1-5. If hematologic dose limiting toxicity occurs at 75% of the original dose of temozolomide, then pevonedistat dose level should be decreased to the next lower dose level. If dose limiting neutropenia recurs after use of growth factor and dose reductions of temozolomide and pevonedistat the patient should be removed from protocol therapy.

6.1.2 For dose-limiting thrombocytopenia, after counts recover, start the next cycle with

a decrease in temozolomide to 75% of the original dose (75 mg/m²/dose) on Days 1-5. Patients should continue to receive the full doses of pevonédistat and irinotecan. If dose limiting thrombocytopenia occurs at 75% of the original dose of temozolomide, then pevonédistat dose level should be decreased to the next lower dose level and the irinotecan should be given at full dose.

6.1.3 Patients who have a dose-limiting hematological toxicity that does not resolve to eligibility parameters within 21 days after the planned start of the next treatment cycle must be removed from protocol therapy.

6.2 Dose Modifications for Non-Hematological Toxicity (for patients \geq 12 months)

6.2.1 Patients who have any dose-limiting non-hematological toxicity (as defined in [Section 5.6.1](#)) may continue on protocol therapy upon meeting eligibility lab requirements or baseline but should receive subsequent doses of pevonédistat at the next lower dose level. Irinotecan and temozolomide should be continued at the same dose.

6.2.2 If the same non-hematological dose-limiting toxicity recurs after one dose reduction, the patient must be removed from protocol therapy.

6.2.3 Patients who have a dose-limiting non-hematological toxicity that does not resolve to baseline or eligibility within 21 days after the planned start of the next treatment cycle must be removed from protocol therapy.

6.2.4 Pevonédistat dose modification for hepatic toxicity:

In all cycles, AST, ALT, and bilirubin should be checked prior to each dose of pevonédistat and then once weekly for the remaining weeks of the study. It is anticipated that LFTs (AST, ALT, and occasionally bilirubin) may be elevated for approximately 48 hours following the end of the 1st pevonédistat infusion. See [Appendix III](#) for toxicity grading table.

For Grade 2 or 3 AST, ALT, or bilirubin on or after Cycle 1 Day 8, pevonédistat should be held. Once the elevated AST, ALT, or bilirubin returns to \leq Grade 1 by the end of the current cycle, then pevonédistat dose may be resumed at the same dose. If a dose is delayed due to increased LFTs, pevonédistat needs to be administered by Day 25 of Cycle 1 or Day 18 of subsequent cycles (within a cycle there should be a maximum of 13 days between doses).

For Grade 4 AST, ALT, or bilirubin on or after Cycle 1 Day 8, the pevonédistat dose should be held for the remainder of the cycle. If the elevated AST, ALT, or bilirubin return to \leq Grade 1, then pevonédistat may be restarted at the next cycle at the next lower dose level.

Interventions for Dose Modifications Secondary to Elevated AST, ALT, or bilirubin	
Grade 2	Hold pevonédistat until resolved to \leq Grade 1
Grade 3	Hold pevonédistat until resolved to \leq Grade 1
Grade 4	Hold pevonédistat for remainder of cycle. For subsequent cycle resume at next lower dose level if resolved to \leq Grade 1
For pevonédistat, a minimum of 1 full calendar day between any 2 doses should be maintained, and a maximum of 3 doses of pevonédistat within Cycles 2+ must not be exceeded. There should be a maximum of 13 days between doses within a given cycle.	

6.2.5 Pevonedistat dose modification for hypophosphatemia:

If hypophosphatemia is \geq Grade 3, study drug treatment should not be resumed until the hypophosphatemia is \leq Grade 2. Hypophosphatemia should be evaluated (including severity and etiology), monitored, and treated according to institutional guidelines.

6.3 Dose Modifications for Non-Hematological Toxicity (for patients < 12 months at the time of the DLT)

Patients less than 12 months of age who have a \geq Grade 2 non-hematological toxicity attributable to the study drug will have pevonedistat held as per [Section 6.2](#) and this will be considered a DLT with the specific exclusion of Grade 2 liver enzyme elevation, including ALT/AST/bilirubin, that returns to Grade \leq 1 or baseline prior to the time for the next treatment cycle (see [Section 6.2.4](#)). Patients should receive subsequent cycles of the drug but with dose modifications according to [Section 6.2](#).

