1.0 GOALS AND OBJECTIVES (SCIENTIFIC AIMS)

1.1 Primary Aims

- 1.1.1 To estimate the maximum tolerated dose (MTD) and/or recommended Phase 2 dose (RP2D) of pevonedistat administered as an intravenous infusion on Days 1, 8, 10, and 12 of a 28-day cycle (Cycle 1), and on Days 1, 3, and 5 of a 21-day cycle (Cycle 2 and beyond) in combination with irinotecan (administered as an intravenous infusion on Days 8-12 of Cycle 1 and Days 1-5 of Cycles 2+) and temozolomide (administered orally on Days 8-12 in Cycle 1 and Days 1-5 of Cycles 2+) in children with recurrent or refractory solid tumors, including CNS tumors and lymphoma.
- 1.1.2 To define and describe the toxicities of pevonedistat administered on this schedule.
- 1.1.3 To characterize the pharmacokinetics of pevonedistat in children with recurrent or refractory cancer.

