2.5 Overview of Proposed Pediatric Study

This is a phase 1 dose escalation of pevonedistat as a single agent and in combination with irinotecan and temozolomide for patients with refractory or recurrent solid tumors, including CNS tumors and lymphoma. Pevonedistat will be administered in combination with IV irinotecan and PO temozolomide in a 28-day cycle for Cycle 1 and 21-day cycles thereafter in Part A1 (patients \geq 12 months and \leq 21 years). Part A2 will enroll infants (\geq 6 months to < 12 months) one dose level behind the dose level at which the patients in Part A1 are enrolling, in order to maximize the safety for infant subjects. Pharmacokinetics will be obtained in all patients (see [Section 8.3](#)). Pharmacodynamic studies will be obtained in consenting patients (see [Section 8.4](#)).

A cycle of therapy is considered to be 28 days for the first cycle and 21 days for cycles thereafter. A cycle may be repeated 17 times, up to a total duration of therapy of 12 months.

Pevonedistat will be administered IV over 1 hour on Days 1, 8, 10, and 12 of a 28-day cycle for Cycle 1, and on Days 1, 3, and 5 of a 21-day cycle for Cycle 2 and beyond. After the initial dose of pevonedistat (Cycle 1 Day 1), subsequent doses will be given in conjunction with irinotecan and temozolomide. The MTD in adult phase 1 studies in adults given in combination with standard chemotherapy with advanced solid tumors treated on this schedule is 20-25 mg/m². Since in this study pevonedistat will be combined with irinotecan and temozolomide, a relatively well-tolerated regimen, the starting dose will be 15 mg/m², 75% of the adult MTD. Part A2 will open to enrollment on Dose Level 1 (15 mg/m²) once Part A1 has escalated to Dose Level 2 (20 mg/m²). In order to obtain single agent PK data, pevonedistat will be given as a single dose one week prior to initiating combination therapy with irinotecan and temozolomide.

The industry partner does not have plans to develop pevonedistat as a single agent in

pediatrics. Thus, this study is designed to determine the safety and pharmacokinetics of pevoneditstat alone and in combination with irinotecan and temozolomide.

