2.6 Rationale for Amendment #5 (addition of dose level 4)

[figure not shown]
Pevoneditstat, a first in class inhibitor of NEDD8 activating enzyme (NAE), prevents the activation of Cullin-RING ligases (CRL) necessary for proteasome mediated degradation of key regulatory proteins important in cell survival. In adults with solid tumors, the maximum tolerated dose (MTD) in combination with chemotherapy is 20-25 mg/m².^{28,29}

As a single agent in adults with MDS/AML the MTD for pevoneditstat infusions on days 1, 3, and 5 per cycle was determined to be 59 mg/m² and for melanoma or advanced solid tumors, was determined to be 67 mg/m². The recommended phase 2 dose for pevoneditstat monotherapy for that schedule is 50mg/m².^{1,30} In adults, the predominant dose limiting toxicity (DLT) was hepatotoxicity.

In our current Phase 1 Study of Pevoneditstat (MLN4924) a NEDD8 Activating Enzyme Inhibitor, in Combination with Temozolomide (TMZ) and Irinotecan (IRN) in Pediatric Patients with Recurrent or Refractory Solid Tumors (ADVL1615), 18 patients have enrolled and all were eligible and evaluable for cycle 1 dose limiting toxicity (DLT) assessment. Six patients each enrolled on pevoneditstat dose levels 1 (15mg/m²), 2 (20mg/m²), and 3 (25mg/m²). No pediatric patients experienced a DLT, and only 1 patient each experienced grade 3 elevated AST and elevated ALT, which resolved and did not meet criteria for dose-reduction.³³

The pharmacokinetics (PK) of pevoneditstat were similar in adult and pediatric studies. In our pediatric study, the mean area under the curve (AUC) at the 25 mg/m² dose level on day 8 (in combination with irinotecan and temozolomide) was 1296 hr•ng/mL, half-life (T $\frac{1}{2}$) was 5-6 hours, time to maximum concentration (Tmax) was 1 hour, and average clearance was 20 L/hr/m², comparable with adult trials (Figure 1).³¹ Both AUC and maximum concentration (Cmax) increased with dose level, but unlike the adult data, the increase appeared to be greater than dose-proportional. This was reflected in the Day 1 clearance which showed a small decrease with dose suggesting non-linear clearance.

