8.3.2.1 All patients

For patients ≥ 10 kg, samples will be obtained at the following time points:

Day 1 of Cycle 1: pre-dose, end of pevonedistat infusion, and at 1, 2, 4, 6-8 and 24 hours post-dose infusion.

Day 8 of Cycle 1: pre-dose, end of pevonedistat infusion, and at 1, 2, 4, 6-8 and 24 hours post-dose infusion.

Day 10 of Cycle 1: pre-dose

For patients < 10 kg, samples will be obtained at the following time points:

Day 1 of Cycle 1: pre-dose; end of infusion; and at 2, 6-8, and 24 hours post-dose infusion.

Day 8 of Cycle 1: pre-dose; end of infusion; and at 2, 6-8, and 24 hours post-dose infusion.

Day 10 of Cycle 1: pre-dose

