NOTE: PCP prophylaxis should start on Cycle 1 Day 8, given twice daily for 3 consecutive days a week (i.e., BID Friday, Saturday, Sunday), every week or per institutional practice, until the end of protocol therapy. See [Section 5.1](#) for details.

Assigned Dose Level _____			Ht _____ cm	Wt _____ kg	BSA _____ m ²		
Date Due	Date Given	Day	Pevonedistat mg	TEMO mg	IRIN mg	Cefixime mg	Studies
		PRE					a - m, n*, o, p
		1	mg				h, m, n*
		...					
		4					e
		5					
		6				mg	
		7				mg	
		8	mg	mg	mg	mg	b, e - h, m, n*
		9		mg	mg	mg	
		10	mg	mg	mg	mg	h, m, n*
		11		mg	mg	mg	
		12	mg	mg	mg	mg	e, h
		13				mg	
		14				mg	
		15				mg	b, e - h
		...					
		19					e
		...					
		22					b, e - h
		...					
		26/-1					e
		27/0				mg	
		28/1				mg	a - h, j - k, l^, p
			Following completion of Cycle 1, Cycle 2 starts on Day 28 or when starting criteria are met (see Section 5.3), whichever occurs later.				

* For consenting patients only.

^ Study may be obtained within 72 hours prior to the start of the subsequent cycle.

See [Section 6.0](#) for Dose Modifications for Adverse Events and [Section 7.0](#) and the COG Member website for Supportive Care Guidelines.

Version Date: 08/27/2020

Page 98

Required Observations in Cycle 1

All baseline studies must be performed within 7 days prior to enrollment unless otherwise indicated below. See [Section 8.0](#) for schedule of assessments.

- a. History
- b. Physical exam with vital signs: Vital signs should be checked prior to each pevonedistat infusion. Vital signs will be also be assessed at the end of treatment.
- c. Height, weight, BSA
- d. Performance status
- e. CBC, differential, platelets: Twice weekly during Cycle 1. If patients have Grade 4 neutropenia or thrombocytopenia, CBCs should be checked at least every other day until recovery to Grade 3 or until the criteria for dose limiting toxicity are met.
- f. Electrolytes including Ca⁺⁺, PO₄, MG⁺⁺
- g. Creatinine
- h. ALT, AST, bilirubin: Check prior to each dose of pevonedistat, then weekly for remaining weeks of cycle. If patients have Grade 2, 3, or 4 ALT/AST/bilirubin on or after Cycle 1 Day 8, AST/ALT/bilirubin should be checked at least every other day until recovery to ≤ Grade 1. See [Section 6.2.4](#) for more details.
- i. ECHO/EKG
- j. Albumin, Pulse Oximetry

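### No liver test is scheduled between the Day 1 and Day 8 pre-dose draws, so a transient hepatic DLT after the first pevonedistat dose can go unseen

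*Combined protocol and SAP*

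**What the plan says.** **Dosing.** Primary aim 1.1.1 has pevonedistat "administered as an intravenous infusion on Days 1, 8, 10, and 12 of a 28-day cycle (Cycle 1"). Section 5.1 adds: "In Cycle 1, pevonedistat will be administered as a single agent on Day 1". Irinotecan and temozolomide start on Day 8.

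**Expected liver effect.** Section 6.2.4 anticipates that "LFTs (AST, ALT, and occasionally bilirubin) may be elevated for approximately 48 hours following the end of the 1st" infusion. Section 2.6 notes: "In adults, the predominant dose limiting toxicity (DLT) was hepatotoxicity".

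**Liver-test schedule.** Section 6.2.4 says "AST, ALT, and bilirubin should be checked prior to each dose of" pevonedistat, then once a week. The Section 8.1 footnote agrees, and so does the Cycle 1 delivery map in Appendix XIII-A: "h. ALT, AST, bilirubin: Check prior to each dose of pevonedistat, then weekly for remaining weeks of cycle". After the pre-study row, the map places this item on Days 1, 8, 10, 12, 15, 22 and 28. Its only entry between Days 1 and 8 is a blood count on Day 4. The hepatic hold rules and the every-other-day liver checks begin at Cycle 1 Day 8.

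**DLT rule.** Section 5.6 makes the first cycle the observation period. From 12 months of age, a Grade 3 ALT, AST or bilirubin rise that recovers before the next cycle is excepted, and Grade 4 is not. Under 12 months, only a recovering Grade 2 rise is excepted.

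**Purpose.** Section 2.5 says: "Thus, this study is designed to determine the safety and pharmacokinetics of" the drug alone and in combination. It gives single-agent pharmacokinetics as the reason for the Day 1 dose.

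**The concern.** The protocol names a period in which it expects liver tests to rise, counts that period in the DLT window, and requires no liver test within it. An event that Section 5.6 defines as a DLT can then occur and resolve without any required test showing it. Section 11.2.1 would still treat the patient as evaluable, because it asks only that the appropriate toxicity monitoring be done, and none is scheduled on Days 2-7.

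The toxicity concerned is the one that matters most for this drug. In the adult solid-tumor combination study described in Section 2.3.1, 8 of the 12 patients with DLTs had raised liver tests. Amendment 5 adds a 35 mg/m² level on the strength of observed tolerability, while Section 2.6 says that exposure appeared to rise more than in proportion to dose. Under Section 11.3, two DLTs in a cohort of up to six stop escalation, so one unseen event can change a decision.

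The same gap leaves the safety of the drug alone, a purpose stated in Section 2.5, unmeasured for its predominant adult toxicity at the time the protocol expects it.

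**Working it through.** The 48 hours is a stated expectation. The documents give no inputs from which it could be derived, so the check is one of timing.

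**Inputs.** A 60-minute infusion (Section 5.1); Cycle 1 doses on Days 1, 8, 10 and 12 (Section 1.1.1); a 48-hour window from the end of the first infusion (Section 6.2.4); required liver tests on Days 1, 8, 10, 12, 15, 22 and 28 (Appendix XIII-A, consistent with Section 8.1). Assumption: doses and draws fall at about the same clock time each day. A shift of a few hours does not alter the result.

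**Step 1: the window.** It ends 1 + 48 = 49 hours after the start of the Day 1 infusion, early on Day 3.

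**Step 2: blood draws after the Day 1 dose.**

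| Draw | Hours after end of infusion | Inside 48 h? | Liver test required? |
|---|---|---|---|
| 24-hour PK (Day 2) | 24 | Yes | No |
| Blood count (Day 4 on the map) | 3 × 24 − 1 = 71 | No | No |
| Day 8 pre-dose | 7 × 24 − 1 = 167 | No | Yes |

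Required liver tests on Days 2-7: none. The first falls 167 − 48 = 119 hours (119/24 ≈ 5.0 days) after the window closes. After the Day 8 dose, the Day 10 pre-dose test falls at 2 × 24 − 1 = 47 hours, just inside a window of the same length.

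**Step 3: what can be missed.** From 12 months of age, it is a Grade 4 value (Appendix III: ALT above 900 U/L, AST above 1000 U/L, bilirubin above 10 times ULN) that has dropped below Grade 4 by Day 8. In infants, it is a Grade 3 or 4 value (ALT from 226 U/L, AST from 251 U/L, bilirubin above 3 times ULN) that has dropped below Grade 3 by Day 8. A rise at those grades that persists to Day 8 is found.

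**Step 4: sensitivity of the two-in-six rule (illustration with assumed rates).** Let q be the rate of all other DLTs and g the rate of transient hepatic DLTs that go unseen. Assume independence and six evaluable patients. If hepatic events are unseen, p = q; if seen, p = 1 − (1 − q)(1 − g). Then P(2 or more of 6) = 1 − (1 − p)^6 − 6p(1 − p)^5.

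| q | g | p if seen | P(stop), unseen | P(stop), seen |
|---|---|---|---|---|
| 0.10 | 0.05 | 0.145 | 0.114 | 0.212 |
| 0.10 | 0.10 | 0.190 | 0.114 | 0.320 |
| 0.10 | 0.20 | 0.280 | 0.114 | 0.536 |

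For q from 0.05 to 0.15 and the same values of g, P(stop) runs from 0.033 to 0.224 unseen and from 0.109 to 0.622 seen. Neither q nor g is in the documents. The table shows only that the rule is sensitive if such events occur.

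**The case against.** The strongest reply is that the gap is deliberate and harmless. The Day 1 dose was added for pharmacokinetics. The paragraph that anticipates the early rise starts its hold rules at Day 8, which suggests that the rise is tolerated, and the Day 8 pre-dose test checks recovery before combination therapy. Appendix XIII-A allows other tests as good clinical care. Section 2.6 reports 18 evaluable patients at 15-25 mg/m² with no DLT and one patient each with Grade 3 AST and ALT, on a schedule that does test at about 47 hours after the Day 8 and Day 10 doses.

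Much of this stands. It limits the likely size of the problem, and the 20% hepatic rate in the illustration looks high beside it: with 0 of 18, the one-sided 95% upper limit is 1 − 0.05^(1/18) = 15.3%, pooled over three dose levels. It does not close the gap. No section says that the early rise is tolerated or that Days 2-7 lie outside hepatic DLT ascertainment. Discretionary tests are not systematic. If the same schedule applied to those 18 patients, their count cannot speak to Days 2-7, and it contains no one at 35 mg/m² and no infant.

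A reader might infer that the trial will wrongly attribute pevonedistat's own liver effect to the combination, because the two are sampled at different times after dosing. The documents do not support that. No single-agent versus combination comparison is planned, Section 11.3 promises only a descriptive summary of toxicities, and Sections 13.4.1-13.4.2 keep only the worst grade of an event per cycle.

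**Conclusion.** The gap is confirmed. None of the anticipated 48-hour window after the first dose is covered by a required liver test, in any patient at any dose level. A hepatic DLT as defined in Section 5.6 can be missed if it subsides before Day 8.

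The consequence is bounded. From 12 months of age, only transient Grade 4 events are affected. In infants, transient Grade 3 events are too, but Section 11.1 records that none had enrolled in Part A2 as of 6/30/19. A reader might infer that the MTD is materially wrong. The documents give no rate for such events and do not support that conclusion. The finding rests on the stated 48-hour expectation and on the required schedule, without counting tests done at a site's discretion. It is an inexpensive improvement to ascertainment and needs no redesign.

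**What to change.** 1. In Section 8.1 and Appendix XIII-A, add ALT, AST and bilirubin to the 24-hour pharmacokinetic draw after the Day 1 dose. Section 8.3.2.1 already requires it at every body weight ("Day 1 of Cycle 1: pre-dose, end of pevonedistat infusion, and at 1, 2, 4, 6-8 and 24 hours post-dose infusion" from 10 kg, with a shorter list below 10 kg that keeps the 24-hour sample). It lies inside the anticipated window and needs no new venipuncture. It samples that window at a single time, so it narrows the gap without guaranteeing that the peak is seen.
2. Liver tests on the mid-week blood-count draw are optional. At about 71 hours they would show recovery only and do not substitute for item 1.
3. State in Section 11.3 that Days 1-7 liver values will be summarized descriptively by dose level and age part, from dated laboratory results. Adverse event forms will not serve, because they hold only the worst grade per cycle. Confirm that the case report forms capture those dates and values.
4. Reconcile Sections 5.6, 6.2.1 and 6.2.4 (and Section 6.3, which refers infants to 6.2) on a hepatic DLT found before Day 8. Section 6.2.1 attaches a consequence to any non-hematological DLT, while the hold rules in 6.2.4 begin at Day 8. The added test is therefore not a matter of ascertainment alone. No management rule is proposed here.

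**Cost.** One schedule entry and one chemistry result per patient. The extra blood volume is small but matters most in infants: Appendix II already lists 22-33 mL of PK sampling below 10 kg, and Section 8.3.4 commits all the PK plasma to two aliquots. More transient values will be recorded, and a DLT may be counted that would otherwise have been missed. The change helps only patients still to be enrolled.
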